3.0 Study design

This is a cross-sectional diagnostic accuracy study that includes both participants and health worker participants. Health workers will include trained intended users of the G6PD tests. Health workers will take capillary blood samples and conduct POC G6PD testing on participant samples. Results will be compared to a reference assay. Trained health workers will also be surveyed to assess product usability through a questionnaire to assess label and packing comprehension as well as results interpretation for simulated G6PD tests.

Study endpoints include:

- Diagnostic performance (sensitivity and specificity) of POC G6PD test compared to reference assay
 - Accuracy between POC G6PD test measure of G6PD activity and a reference assay
 - Accuracy between POC G6PD test measure of hemoglobin and a reference assay
- Comparison of POC G6PD test results using capillary and venous samples
- Percent of trained health workers who can accurately comprehend key messaging included in the test packaging and labels
- Percent of trained health workers who can accurately interpret the result output and classify results as either normal, invalid, deficient or intermediate

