3.1 Statistical analyses

Data will be entered into a Microsoft Excel database with built-in validation rules to minimize data entry errors. Descriptive statistical analysis, including calculating point estimates, distribution, and frequencies of responses, will be used to summarize and characterize the study population.

3.1.1 Diagnostic accuracy and performance:

For the purposes of this study, an individual will be considered G6PD deficient (case) if they test positive by the spectrophotometric gold standard. The primary success criterion will be focused on the ability to identify G6PD deficient participants correctly, such that both the POC G6PD test and the spectrophotometric gold standard test should both accurately identify all G6PD deficient specimens (with < 20% normal) as deficient.

The performance of the POC G6PD against the spectrophotometric gold standard will be determined by calculating the sensitivity and specificity. Sensitivity and specificity of the SD Biosensor (SDB) G6PD assay were calculated as per Domingo et al. [14]. In summary, an adjusted male median will be calculated for both the POC G6PD and spectrophotometric gold standard test from where the 30%, 40%, 70% and 80% cutoff levels for the two tests will be used to categorically define G6PD deficient cases.

Sensitivity calculations will be determined by the following method: TTP=true and test positive (positive by reference assays according to case definition and positive by the POC G6PD test), FNTP=false negative true positive (positive by reference assays according to case definition and negative by the POC G6PD test). Sensitivity = $TTP/(TTP+FNTP)$.

Specificity will be determined by the following method: TPTN=test positive true negative (negative by reference assays according to case definition and positive by POC G6PD test), TTN=Test and true negative (negative by reference assays according to case definition and negative by POC G6PD test). Specificity= $TTN/(TTN+TPTN)$.

Sensitivity and specificity results will be reported using 95% confidence intervals.

3.1.2 Accuracy between G6PD activity and Hemoglobin methods:

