Quantitative agreement for both G6PD activity and Hb values between the POC G6PD test and spectrophotometric gold standard will be graphically analyzed. Correlation graphs between the POC G6PD test and gold standard test will be plotted and an R-squared value will be determined. An R-squared value of greater than 0.9 for both G6PD activity and Hb will be considered acceptable.

Bland Altman plots, where differences between the G6PD POC tests and gold standard test are plotted against the gold standard value, together with the 95% limits of agreement. Acceptable limits of agreements for Hb should be within +/-1.0 g/dL (based on a 6% estimate for allowable method bias) and for G6PD activity should be within +/-2.0 U G6PD/g Hb (based on a 15% estimate for allowable method bias). All statistical analyses will be performed using Stata 13.0.

The data comparison for the analyses is outlined below:

Table 1. Comparison methods

Index test by sample type	Reference method	
	G6PD normalized for Hb	Hb
Venous	Point Scientific G6PD from venous specimen normalized for Hb from venous specimen	Hb from venous specimen
Capillary		Hemocue Hb from finger stick

3.1.3 Diagnostic usability:

Response choices to usability assessment questionnaires will include both multiple-choice and open-ended responses. The usability questionnaire will include a brief assessment of health literacy using a validated health literacy instrument. Participants will be encouraged to comment on any aspects of the label or results they find confusing or inadequate. Success criteria are defined as 85% correct participant response to questions that assess key messages and results interpretation. Any participant that obtains 85% or above correct responses to the usability questionnaire will be considered to accurately comprehend the product IFU and labelling. Analyses will include descriptive statistics and a tabular presentation of findings.

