5.2.5 Testing procedures in the laboratory

At the laboratory, aliquots of the venous blood sample will be used to run an additional replicate of the SBD POC test and reference tests in duplicate. Depending on availability, additional POC G6PD tests that are both commercially available and currently under development may be run as well. Hemoglobin [Hb value (g/dl)] will be determined within 24 hours using a hematology analyzer for each sample to estimate the G6PD activity. Aliquots of the venous blood will be used for running the spectrophotometric assay (reference standard) and the fluorescent spot test (FST). The reference assay, hemoglobin, and replicate of the G6PD quantitative test will be conducted at the same time. A thermometer and a hygrometer will be placed at the study site near the assays. Temperature and humidity will be observed at the time the tests are run and recorded in the study database.

[figure not shown]
Test operators in the laboratory will be blinded to the results of the POC tests obtained and recorded in the field and operators of the reference assay will be blinded to the results of the replicate POC test run on venous sample. If there is a discrepancy between the results of the reference assay replicates, greater than allowed by the TPP, testing will be repeated. Performance characteristics and the results of additional testing of samples with discrepant results will be reported as per WHO technical specifications [15].

Leftover sample will be stored for possible confirmatory or additional testing. Depending on availability of additional novel G6PD tests at the time of study start, additional assays may be run on remaining samples. If additional POC G6PD tests are added, in particular tests that are under investigation and not registered for use in Brazil, the study team will amend the protocol and advise the ethical review boards and appropriate regulatory authorities. For all novel assays to be included in the study, appropriate regulatory procedures will be followed in order to include the assays for research purposes only.

This includes products that not yet commercially available and products that are commercially available but are not part of the standard of care at the clinic site. In the event the stored sample is used, the Fundação de Medicina Tropical [name] Dourado (FMT/HVD) and Fiocruz will be responsible for obtaining the necessary ethical approvals.

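### The acceptance limits for the 95% limits of agreement rest on a bias allowance with no stated level and no part for scatter, and no separate or level-specific criterion judges bias

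*Combined protocol and SAP*

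**What the plan says.** Section 3.0 lists "Accuracy between POC G6PD test measure of G6PD activity and a reference assay" as an endpoint, and a matching one for hemoglobin. Section 3.1.2 gives the only acceptance rules for them:

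- Correlation: "An R-squared value of greater than 0.9 for both G6PD activity and Hb will be considered acceptable".
- Bland-Altman plots in which "differences between the G6PD POC tests and gold standard test are plotted against the gold standard value", with 95% limits of agreement. For G6PD the acceptable limits are set out as "for G6PD activity should be within +/-2.0 U G6PD/g Hb (based on a 15% estimate for allowable method bias". For Hb they should be "within +/-1.0 g/dL (based on a 6% estimate for allowable method bias".

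The section names no activity or Hb level for either percentage, no imprecision component and no source. It sets no acceptance limit for the mean difference itself. Both rules are stated for the sample as a whole. Section 3.2 expects roughly 100 deficient and 200 intermediate participants among 2,000.

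**The concern.** Method bias is the mean difference between two methods. The 95% limits of agreement are that mean plus and minus 1.96 SD of the differences. An allowance for the first is not, by itself, a basis for a bound on the second.

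Two things follow. A device whose bias is within the stated allowance may fail because of scatter that the allowance never covered. And a single pooled rule, in a sample that is mostly normal, says little about bias at low activity, where a quantitative G6PD reading matters most. Section 2.0 says the results will support WHO prequalification and product registration, so the sponsor needs to know what a finding of acceptable agreement means.

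**Working it through.** **Inputs.** Limits +/-2.0 U/g Hb and +/-1.0 g/dL, with 15% and 6% (section 3.1.2). G6PD levels 2.8, 6.5, 7.4 and 9.3 U/g Hb for 30%, 70%, 80% and 100% (Table 7, an earlier laboratory evaluation). Hb thresholds 7.0, 10.0, 11.9 and 12.9 g/dL (section 5.6). Expected mix 5% deficient, 10% intermediate, 85% normal (section 3.2). The documents give no SD of differences, so the SDs below are assumptions.

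**1. Trying to reproduce the limits: percentage x level.**

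- G6PD: 0.15 x 2.8 / 6.5 / 7.4 / 9.3 = 0.42 / 0.98 / 1.11 / 1.40. None is 2.0.
- Hb: 0.06 x 7.0 / 10.0 / 11.9 / 12.9 = 0.42 / 0.60 / 0.71 / 0.77. None is 1.0.
- Solving back: 2.0 / 0.15 = 13.3 U/g Hb, and 1.0 / 0.06 = 16.7 g/dL. Neither level is in the documents.
- Reading the percentage as a CV of the difference needs 2.0 / (1.96 x 0.15) = 6.8 U/g Hb and 1.0 / (1.96 x 0.06) = 8.5 g/dL, which are not printed levels either.

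**2. Scatter left once the bias allowance is used.** Largest SD = (limit - bias) / 1.96.

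| Analyte and assumed level | Bias | Largest SD of differences |
|---|---|---|
| G6PD, no bias | 0 | 2.0 / 1.96 = 1.02 |
| G6PD, 15% at 9.3 | 1.395 | 0.605 / 1.96 = 0.31 |
| G6PD, 15% at 13.3 | 2.0 | 0 |
| Hb, no bias | 0 | 1.0 / 1.96 = 0.51 |
| Hb, 6% at 12.9 | 0.774 | 0.226 / 1.96 = 0.12 |

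Example: a constant bias of 1.395 with SD 0.5 gives 1.395 +/- 0.98, or 0.42 to 2.38. It is within 15% at 9.3 and fails +/-2.0.

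**3. Bias confined to deficient samples.** Take +1.4 U/g Hb in the 5% who are deficient, none elsewhere, and SD 0.5 within each class.

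- Pooled mean = 0.05 x 1.4 = 0.07.
- Pooled variance = 0.5^2 + 0.05 x 0.95 x 1.4^2 = 0.250 + 0.093 = 0.343, so SD = 0.586.
- Limits = 0.07 +/- 1.96 x 0.586 = -1.08 to 1.22, well inside +/-2.0.
- R-squared by simulation is 0.94 to 0.96, which passes. This assumes deficient values uniform below 30% of 9.3, intermediate values uniform from 30% to 80%, and normals with mean 9.3 and CV 15% to 25%.
- Yet 1.4 / 2.8 = 50% of the reading at the top of the deficient range, and more below it. The limit of 2.0 is itself 71% of 2.8.

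**4. R-squared.** Adding a constant to every device reading leaves R-squared unchanged, and a proportional bias with the same scatter does not lower it. It also depends on spread. Under the same assumptions, an unbiased device exactly at +/-2.0 (SD 1.02) gives 0.85 to 0.90 in the planned mix, and 0.89 to 0.91 with 200 in each abnormal group. For Hb, an unbiased device at +/-1.0 has R-squared = S^2 / (S^2 + 0.51^2), which exceeds 0.9 only if the sample SD S is above 3 x 1.0/1.96 = 1.53 g/dL. The documents do not give S.

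**The case against.** The strongest reply is that limits of agreement already control bias, since a pass requires |bias| to be at most 2.0 - 1.96 SD. With SD 0.5 that is 1.02 (11% of 9.3), and with SD 0.7 it is 0.63 (7%). At 9.3, any pass with SD above 0.31 therefore meets the 15% allowance overall. This is right. A reader might infer that the plan has no control of bias, or that a pass says nothing about the overall allowance; the documents do not support either reading. The constant-bias example in the working fails the plan's rule, so there the rule is strict rather than lax. The reply does not reach bias by level, because the implicit bound applies only to the pooled mean.

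It can also be said that "based on" does not claim 2.0 = 15% of 9.3. That too is fair. The 9.3 comes from earlier laboratory data, the study will compute its own adjusted male medians, and section 3.1.2 ties 15% to no level. A reader might call this a calculation error, but no printed calculation is wrong. What is missing is the step from the percentage to the limit.

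Finally, the R-squared ranges rest on assumed distributions, and the assumed CV moves them about as much as the sample mix does. They illustrate direction and are not predictions.

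**Conclusion.** The point holds as an unsupported basis for a decision threshold. The printed limits cannot be derived from the stated percentages at any level in the documents, and they bound bias plus scatter while being justified by bias alone. A device within its allowance can fail through scatter: at an assumed 9.3 U/g Hb the tolerable SD falls from 1.02 to 0.31. A device with a bias of 50% or more in deficient samples can pass both rules (assumed SD 0.5, planned 5/10/85 mix). The limits are therefore neither simply loose nor simply tight. The first result depends on the level assumed and the second on the SD and class distributions assumed. That the limits cannot be derived depends on neither.

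A reader might infer that the primary result is at risk. The documents do not support that. Classification uses cutoffs for which "an adjusted male median will be calculated for both the POC G6PD and spectrophotometric gold standard test", so each test is scaled to its own median. Sensitivity, specificity, the primary criterion and the sample size do not use these limits. Only the quantitative accuracy endpoints for G6PD activity and Hb are affected. The change should be made, but the study does not depend on it.

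**What to change.** Amend section 3.1.2 as follows.

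1. Apply the 15% and 6% allowances to the mean difference, with 95% CIs. State the level at which each applies. Report overall and by activity class, and by Hb band for Hb.
2. Report the 95% limits of agreement separately. Give any acceptance limit for them its own basis, covering bias plus scatter.
3. Make R-squared descriptive.

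One caution on class means: if the same reference reading sets the class and enters the difference, an unbiased test shows a small false bias (about 0.1 U/g Hb in the deficient and intermediate classes, assuming error SDs of 0.5 for the reference and 0.7 for the device). The laboratory will already "run an additional replicate of the SBD POC test and reference tests in duplicate", so taking class from one replicate and the difference from the other is a simple sensitivity analysis. Both runs must be kept where section 5.2.5 triggers a repeat. The capillary Hb comparator is "Hemocue Hb from finger stick", for which no duplicate is described, so there the limitation should be stated. Deming or errors-in-variables regression of bias on level is optional.

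The cost is a few sentences and one estimate with CI per class and analyte, with no new samples. Precision is adequate: at an assumed SD of 0.7 the CI half-width is 1.96 x 0.7 / sqrt(n), or 0.14 for n = 100, 0.10 for n = 200 and 0.03 for n = 1,700. The downside is slightly more analysis and an explicit bias criterion that the device could fail.

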Evaluation of a diagnostic to identify G6PD deficiency in Brazil

Version 5
May 2019

Investigators:

Location of Research:

Manaus and Porto Velho, Brazil

Proposed Project Dates:

May-December 2019

Study Title	Validation of diagnostics to identify G6PD deficiency in Brazil
Précis	Cross-sectional diagnostic accuracy study with 2,000 patient participants and 15 health worker participants. The participant population will be recruited at clinics and through a household survey using an enriched sample of a population with known G6PD status, established through previous epidemiological studies. The health worker participants will include trained intended users of the G6PD tests. Health workers will take capillary blood samples and conduct two point of care tests: 1) hemoglobin test, and 2) investigational point-of-care (POC) G6PD test. A thick blood slide will also be prepared for malaria microscopy. Venous blood will be collected and transferred to a laboratory where reference assays will be performed on venous samples using the Pointe Scientific G6PD Analyzer and hemoglobin tests. Trained health workers will also be surveyed to assess product usability through a questionnaire to assess label and packing comprehension as well as results interpretation.
Objectives	
Primary Objective: To assess the accuracy and reliability of G6PD tests in detecting G6PD activity and classifying results when used by trained health care workers in Brazil.
 
Component Objectives:
 
 • To determine the performance of G6PD tests in detecting G6PD activity and hemoglobin (Hb) compared to a reference assay • To assess the comprehension of the G6PD test packaging and labelling among intended users • To assess the usability of G6PD test result outputs among intended users

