7.2 Pointe Scientific

The Pointe Scientific will serve as the reference assay to assess G6PD activity. Its intended use is for the quantitative, kinetic determination of G6PD in blood at 340 nm. For in vitro diagnostic use only.

- A spectrophotometer capable of measuring at 340 nm with temperature controlled cuvette compartment is required to perform the assay
- To determine G6PD activity, which is reported in terms of grams of Hb or the number of RBCs, the Hb or RBC count must be determined separately from performing the G6PD assay. Calculations are then performed to obtain the G6PD activity. For purposes of this study, the G6PD activity from the Pointe Scientific kit will be calculated in terms of grams of Hb.
- US FDA cleared: k024006, Regulatory Class II, Product Code JBF.
- Approved as the predicate device for POC G6PD test evaluation by the US FDA.

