7.4 HemoCue

The HemoCue Hb 301 system is designed for quantitative POC whole blood Hb determination in primary care using a specially designed analyzer, the HemoCue Hb 301 Analyzer, and specially designed microcuvettes, the HemoCue Hb 301 Microcuvettes. The HemoCue Hb 301 System consists of a small and portable analyzer (photometer) and plastic microcuvettes. The microcuvette serves both as a pipette and as a measuring cuvette. A blood sample is drawn into the cavity by the capillary action. The filled microcuvette is inserted into the HemoCue Hb 301 Analyzer. The measurement takes place in the analyzer, which measures the absorbance of whole blood at a Hb/HbO₂ isobestic point. The system is factory calibrated and needs no further calibration.

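### Section 3.1.2 and its Table 1 name different Hb references, and no direct comparison of capillary POC Hb with laboratory Hb is planned

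*Combined protocol and SAP*

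**What the plan says.** The text of section 3.1.2 frames the analysis this way: "Quantitative agreement for both G6PD activity and Hb values between the POC G6PD test and spectrophotometric gold standard will be graphically analyzed". Two Hb criteria follow. For correlation: "An R-squared value of greater than 0.9 for both G6PD activity and Hb will be considered acceptable". For the Bland-Altman analysis: "Acceptable limits of agreements for Hb should be within +/-1.0 g/dL (based on a 6% estimate for allowable method bias".

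The section then sends the reader to Table 1 for the actual comparisons. Hb has its own column there. The venous POC result is paired with Hb from the venous specimen, with no device named. The capillary POC result is paired with "Hemocue Hb from finger stick".

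Other parts of the protocol bear on this:

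- Section 7.2, on the Pointe Scientific assay: "the Hb or RBC count must be determined separately from performing the G6PD assay".
- The Précis counts the bedside hemoglobin test among the point-of-care tests. On the reference side it says "Venous blood will be collected and transferred to a laboratory where reference assays will be performed on venous samples", and it includes hemoglobin tests among those assays.
- Section 7.4 describes HemoCue as "designed for quantitative POC whole blood Hb determination in primary care".
- Section 5.2.4 takes the POC G6PD test and the POC hemoglobin test from one finger stick of at most 30 µl, with a second stick only after an invalid result.
- Section 5.2.5 provides hematology-analyzer Hb for each sample within 24 hours, and a replicate of the POC test on venous blood in the laboratory.
- Section 3.0 lists as endpoints the accuracy of POC Hb against a reference assay and a capillary-versus-venous comparison of POC results.

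**The concern.** Two things look wrong. First, the text and the table disagree about what the Hb criteria are tested against, and the assay named in the text gives no Hb value. Table 1 offers two candidate comparisons. The plan does not say whether both must pass, or what follows if one passes and the other fails, so that choice could be made after the results are known.

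Second, the endpoint calls for a reference assay, yet the finger-stick result, which is the one produced in intended use, is compared only with another point-of-care device reading the same finger stick. Agreement between the two shows that they agree with each other. It does not show that either is close to laboratory Hb. At stake is whether the study can support a statement about capillary Hb accuracy in the WHO prequalification and registration submissions named in section 2.0.

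**Working it through.** **1. The plan's own figure.** The Hb limit is 1.0 g/dL, said to rest on 6%. Setting 0.06 × Hb = 1.0 gives Hb = 16.7 g/dL. The documents do not say at what Hb level the 6% applies, so the figure cannot be reproduced from their inputs. At the adult anemia boundaries in section 5.6 (about 12 g/dL for women, 13 for men), 6% is 0.72 and 0.78 g/dL, and 1.0 g/dL is 8.3% and 7.7%. This is a side point, but the level should be stated.

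**2. The Hb comparators side by side.**

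| POC Hb result | Comparator in the text of 3.1.2 | Comparator in Table 1 | Laboratory Hb available (5.2.5) |
|---|---|---|---|
| Venous | spectrophotometric assay (no Hb output, 7.2) | venous Hb, device unnamed | analyzer |
| Capillary | spectrophotometric assay (no Hb output, 7.2) | finger-stick HemoCue | analyzer, not used for this comparison |

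**3. What the limit allows.** With zero bias, 1.96 × SD of differences ≤ 1.0, so the standard deviation (SD) of differences can be at most 1.0/1.96 = 0.51 g/dL.

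**4. HemoCue bias.** Let c be HemoCue's mean difference from the analyzer. Then POC bias against the analyzer = POC bias against HemoCue + c. A POC test with zero bias against HemoCue has bias c against the laboratory. At c = +0.5 g/dL (assumed), that is half the allowed limit, and the planned capillary comparison would show none of it.

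**5. Independent HemoCue error.** This works the other way, because it is charged to the POC test: allowed POC SD = √(0.51² − HemoCue SD²). The HemoCue SDs are assumptions.

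| HemoCue SD (g/dL) | Allowed POC SD (g/dL) |
|---|---|
| 0 | 0.51 |
| 0.2 | 0.47 |
| 0.3 | 0.41 |
| 0.4 | 0.32 |
| 0.5 | 0.10 |

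The effect is slight at 0.2 and severe at 0.5.

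**6. Error shared by the finger stick.** Assume SDs of 0.3 g/dL for each field device, 0.15 for the analyzer, and s for capillary error common to both field readings. The half-width of the limits against HemoCue is 1.96 × √(0.3² + 0.3²) = 0.83 g/dL whatever s is, because s cancels. Against the analyzer it is 1.96 × √(0.3² + s² + 0.15²), which is 0.66, 0.77, 1.02 and 1.35 g/dL for s = 0, 0.2, 0.4 and 0.6. The HemoCue comparison passes throughout, while the analyzer comparison would miss the limit at the two larger values. Likewise a shared 5% dilution at 14 g/dL (assumed) is 0.05 × 14 = 0.7 g/dL and does not show against HemoCue.

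**7. Reach into G6PD classification.** If dilution scales activity and Hb alike, (0.95 × activity)/(0.95 × Hb) = activity/Hb. Normalised G6PD is unchanged.

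**The case against.** Several stronger readings are tempting, and the documents do not support them.

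- A reader might infer that the Hb limits have no Hb measurement behind them. Table 1 supplies real Hb comparators directly below the text, and someone following it would not compare Hb with the spectrophotometric assay. This part is an inconsistency to reconcile.
- A reader might infer that field Hb is never linked to a laboratory value. The venous POC replicate is compared with venous Hb, most naturally the analyzer's, and capillary versus venous POC results is an endpoint. Together these give an indirect link, although no method or limit is set for the capillary-venous step.
- A reader might tie the gap to health workers specifically. Section 3.0 has health workers running the capillary tests, section 5.2.4 has study staff taking the finger stick, and section 4.1 counts laboratory technicians as health workers. The operators cannot be separated that cleanly.
- A reader might conclude that HemoCue should be replaced as the acceptance comparator. Matching capillary with capillary isolates device disagreement, and a limit justified as allowable method bias fits that use. Moving the limit to finger stick versus venous analyzer adds true capillary-venous variation, which could also fail a good device. Which comparison should carry the criterion is a trade-off.

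It is also fair that the magnitudes rest on assumed errors and that Hb agreement is not the primary success criterion. What stands is that HemoCue is the only direct capillary Hb comparison, and that the criteria are not tied to a named comparison.

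**Conclusion.** The point holds as a cheap improvement. The text and Table 1 disagree on the Hb reference, Table 1 leaves the venous Hb device unnamed, the comparison that carries the R-squared and +/-1.0 g/dL criteria is not fixed, and capillary POC Hb is not compared directly with laboratory Hb although both values will exist.

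The size of any resulting error cannot be stated. The documents give no HemoCue error, capillary-venous difference or analyzer error. The figures in the working steps on HemoCue and shared error only show that the planned comparison can err in either direction. The consequence is confined to the Hb sub-endpoint; a proportional dilution would not by itself move anyone across a G6PD threshold.

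**What to change.** In section 3.1.2 and Table 1:

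1. Correct the wording so that the spectrophotometric assay is the comparator for G6PD activity only.
2. Name the hematology analyzer as the venous Hb reference.
3. State before analysis which comparison or comparisons the R-squared and +/-1.0 g/dL criteria apply to, and the Hb level behind the 6%.
4. Add Bland-Altman analyses of capillary POC Hb versus analyzer Hb and of HemoCue versus analyzer Hb.
5. Keep the same-specimen comparison with HemoCue.

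The cost is wording and two extra plots, from data already collected. The drawback is that limits for capillary POC versus analyzer include true capillary-venous variation; the HemoCue-versus-analyzer plot helps to separate that from device error.
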